18. Diagnosis of another malignancy within 3 years before study treatment, except for superficial skin cancers, or localised, low grade tumours deemed cured and not treated with systemic therapy.

Investigational products, dosage and mode of administration:

- Cabozantinib 40 mg or 20 mg tablets, oral administration, once daily, continuously.
- Atezolizumab 1200 mg administered intravenously, every three weeks (cycle).

Duration of treatment:

All the subjects will be treated with the combination of cabozantinib and atezolizumab until disease progression, unacceptable toxicity or patient consent withdrawal (whichever occurs first).

Reference therapy, dosage and administration:

Not applicable, this is a single arm study that will include patients receiving the same treatment.

Criteria for evaluation:

Efficacy assessments: RECIST V1.1 assessments will be performed on images from CT scans (preferred) or MRI, both preferably with intravenous (i.v.) contrast, of the neck, chest, abdomen (including liver and adrenal glands) and pelvis. Pelvic imaging is recommended only when primary or metastatic disease in the pelvic region is likely. Additional anatomy should be imaged based on signs and symptoms of individual patients at baseline and through follow-up. Baseline assessments should be performed no more than 28 days before the date of inclusion and, ideally, as close as possible to the start of treatment and $q12w \pm 2w$ until objective disease progression/death (whichever comes first). Image assessments by CT scan or MRI may be performed $q8w \pm 2w$ if required by local standard clinical practice or by investigator criteria, as long as the frequency of assessments is maintained. If an unscheduled assessment was performed and the patient has not progressed, every attempt should be made to perform the subsequent assessments at their next scheduled visit.

The primary endpoint definition is as follows:

- **Overall Response Rate (ORR):** includes patients with partial (PR) and complete response (CR) as best response according to RECIST v 1.1.

The efficacy secondary endpoints will be studied as follows:

- **Duration of response (DoR) as per RECIST 1.1:** DOR calculated as the time from the date of first documented CR or PR to the first documented progression or death due to underlying cancer.

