- **Progression-free Survival (PFS):** Median Progression free survival (mPFS) is defined as the time from the date of inclusion to the date of the first documented disease progression or death due to any cause, whichever occurs first. PFS will be determined based on tumour assessment (RECIST version 1.1 criteria). The local Investigator's assessments will be used for analyses. Those patients who are alive and have not progressed at the last follow-up will be censored at the date of the last image available. Patient with no additional image test other than that at baseline will be censored to the day after inclusion.
- **Overall Survival (OS):** Median Overall Survival (mOS) is calculated as the time from date of inclusion to date of death due to any cause.
- **Quality of Life (QoL):** Quality of Life will be analyzed descriptively by QoL questionnaires (EQ-5D-5L, EORTC QLQ-C30 see appendix 2 and 3).

Safety assessments: The assessment of adverse events will include the type of event (including symptoms, physical exam findings and laboratory abnormalities), the incidence, the severity, the timing, the seriousness, and the relatedness regarding the treatment under study. Adverse events will be recorded

and reported in the corresponding section of the case report form. The grade of adverse event will be coded according to the National Cancer Institute's Common Toxicity criteria (NCI-CTCAE v5.0 scoring system). The worst toxicity score will be recorded. In case of SAE and AESI the investigator should immediately fill in the dedicated SAE form and send it by as detailed in section 9.3.2.

Translational substudy (optional):

- **Tumor biopsies:** Collection of the most recent archived, tumor-biopsy sections for identification of predictive biomarkers.
- **Blood samples:** Somatic alterations in tumours including proteomics, transcriptomics, metabolics i.e. metabolic pathways of insulin growth factor, among others. No germinal line determinations will be performed. The levels of IGF-1 in serum (others biomarkers may be analysed) will be measured using the blood samples collected from the patients at the different time-points, according to table 2 "Schedule of assessments". The evolution of biomarkers will be evaluated individually and for the different groups of patients.

Statistical methods:

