5.6. TRANSLATIONAL RESEARCH

- Optional substudy involving tissue biopsies will be performed with samples obtained before treatment, for identification of predictive biomarkers.
- Blood samples: Analysis of somatic alterations in tumours including proteomics, transcriptomics, and metabolics i.e. metabolic pathways of insulin growth factor, among others. No germinal line determinations will be performed. The levels of IGF-1 in serum (others biomarkers may be analysed) will be measured using the blood samples collected from the patients at the different time-points, according to table 2 “Schedule of assessments”. The evolution of biomarkers will be evaluated individually and for the different groups of patients.

Information regarding biological samples collection, management, and shipments are provided in the biological sample manual.

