1.2.2. ENDPOINTS

Primary endpoint:

Overall Response Rate (ORR): includes patients with confirmed partial (PR) and complete response (CR) as best response according to RECIST v 1.1.

Secondary endpoints:

- **Safety profile of cabozantinib and atezolizumab:** The number of patients with AEs and SAEs, changes in laboratory values, vital signs, ECGs, and results of physician examinations graded according to the CTCAE v 5.0. This will be analysed using descriptive statistics techniques such as frequency and contingency tables. The final statistical analysis of this endpoint is expected to be performed within 6 months after database closure, which is expected at 12 months after last patient inclusion. However, interim analysis may be performed when analysing other primary endpoints.
- **Duration of response (DOR) as per RECIST 1.1:** DOR calculated as the time from the date of first documented CR or PR to the first documented progression or death due to underlying cancer.
- **Progression-free Survival (PFS):** Median Progression free survival (mPFS) is defined as the time from the date of inclusion to the date of the first documented disease progression or death due to any cause, whichever occurs first. PFS will be determined based on tumour assessment (RECIST version 1.1 criteria). The local Investigator's assessments will be used for analyses. Patients who are alive and have not progressed at the last follow-up will be censored at the date of the last available image determination (CT Scan or MRI). Patient with no additional image test other than that at baseline will be censored to the day after inclusion.
- **Overall Survival (OS):** Median Overall Survival (mOS) is calculated as the time from date of inclusion to date of death due to any cause.
- **Biomarkers:** To be determined according to study results and Sponsor feasibility.

Sponsor: Grupo Español de Tumores Neuroendocrinos y Endocrinos (GETNE)

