1.3. STUDY METHODS

This is an open labelled, single arm, multicohort phase II multicentre clinical trial of cabozantinib plus atezolizumab in advanced and refractory tumours from endocrine system.

The design includes screening phase, treatment phase (including medical consultation and drug administration Q3w \pm 3 days) unless otherwise specified, disease progression follow up by RECIST 1.1 every 12 weeks, translational research with biopsies and blood samples and long term follow-up.

This is a study with Simon's two-stage design; it requires that an event is observed (confirmed response) in the first nine patients before continuing to the second stage where there is a possible inclusion of 15 additional patients (up to a maximum of 24 patients per cohort).

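### The biomarker endpoint's only definition permits choosing markers after responses are known, and a single arm cannot establish the predictive markers that the protocol seeks

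*Combined protocol and SAP*

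**What the plan says.** Biomarkers are listed among the secondary objectives (synopsis; protocol 4.2, which ties them to an optional translational substudy; SAP 1.2.1) and among the secondary endpoints. The whole definition, in the same words in protocol 10.2.2, SAP 1.2.2 and SAP 2.5.2, is "To be determined according to study results and Sponsor feasibility". Protocol 10.6 leaves full analysis detail to the SAP, but the SAP contains no marker-by-outcome analysis, cut-point, multiplicity rule or results table. Its marker tables (Table 9 and the cohort versions) summarise baseline clinical tumour markers.

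Protocol 5.6 describes two strands of work:

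- **Tissue.** "Optional substudy involving tissue biopsies will be performed with samples obtained before treatment, for identification of predictive biomarkers". The synopsis gives the same aim for archived "tumor-biopsy sections for identification of predictive biomarkers".
- **Blood.** The scope is "proteomics, transcriptomics, and metabolics i.e. metabolic pathways of insulin growth factor, among others". One marker is named: "The levels of IGF-1 in serum (others biomarkers may be analysed) will be measured". Its course is to be described by patient and by group.

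The notes to Table 2 (protocol 8.1) fix the blood samples at baseline, day 1 of cycle 2, and end of treatment or progression. Samples stay at the sites until the end of the study. Protocol 5.1 makes the biomarker study optional, subject to what the sponsor can do, and refers to a biological samples manual for detail.

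On design, the synopsis says under reference therapy: "Not applicable, this is a single arm study that will include patients receiving the same treatment". SAP 1.3 agrees: "This is an open labelled, single arm, multicohort phase II multicentre clinical trial".

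**The concern.** Two separate things are at issue.

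The first is timing. Read plainly, the endpoint sentence lets the results decide what the endpoint is. The trial is open label and the stored blood leaves the sites only at the end, so response will usually be known before assays are run. If markers, cut-points and outcomes are then picked, any nominal association has no error control, yet it would appear under the heading of a secondary endpoint.

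The second is the word predictive. A predictive marker modifies the effect of treatment. Showing that needs patients with and without the treatment at each marker level, and this trial has only the first group. At stake is what the trial may conclude about markers, not whether a cohort is declared positive.

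**Working it through.** **1. The plan's own figure.** None exists for biomarkers. The only sized analysis is objective response (protocol 10.1, SAP 1.4.1): 5% against 20%, 9 then 15 patients, continue on at least 1 of 9, positive on at least 3 of 24. With X1 ~ Bin(9, p) and X2 ~ Bin(15, p), P(X1 ≥ 1 and X1 + X2 ≥ 3) is 0.0931 at p = 0.05 and 0.8047 at p = 0.20. This reproduces the stated one-sided 0.10 and 80% power. No biomarker enters the rule.

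**2. What the endpoint sentence governs.** It does not say what is to be determined. Two readings fit:

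- Results and feasibility decide which markers are analysed. Selection on outcome is then allowed.
- Results and feasibility decide whether the substudy is run at all. Protocol 5.1, which also invokes sponsor feasibility, makes this plausible.

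Under the second reading the markers and outcomes are still undefined if the substudy goes ahead. Under either reading, nothing in the SAP prevents late selection.

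**3. What late selection could cost (illustration).** Assume k independent markers with no true association, each tested at two-sided 5%. P(at least one hit) = 1 − 0.95^k.

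| k (assumed) | P(at least one false hit) |
|---|---|
| 1 | 0.050 |
| 5 | 0.226 |
| 10 | 0.401 |
| 20 | 0.642 |
| 50 | 0.923 |

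Neither k nor the 5% level is in the documents. Positively correlated markers would give lower figures.

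**4. Cut-point freedom in a cohort that just succeeds.** A cohort is positive with 3 responders of 24. Suppose all 3 fall in one marker group and Fisher's exact test is used (the test is assumed). The number of ways to place 3 responders among 24 is C(24,3) = 2024.

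- Split 12/12: two-sided p = 2 × C(12,3)/2024 = 440/2024 = 0.217.
- Split 10/14, responders in the smaller group: C(10,3)/2024 = 120/2024 = 0.059.
- Split 9/15, responders in the smaller group: C(9,3)/2024 = 84/2024 = 0.042.

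Nominal significance is therefore out of reach at an even split and possible only when the smaller group has 9 patients or fewer. In such a cohort the result turns on where the cut is placed.

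**5. Predictive against prognostic.** Write the mean outcome as a + b·m + c·t + d·m·t, with m the marker and t the treatment. The prognostic effect is b and the predictive effect is d. Here t = 1 for everyone, so the mean is (a + c) + (b + d)·m. Only the sum b + d can be estimated. More patients do not help: with the maximum of 144 pooled, an assumed 72/72 split and assumed response rates of 30% and 10%, power for an association is about 83%, but the association is still b + d.

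**The case against.** The case for leaving the text alone has substance.

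- The trial calls itself exploratory, the substudy is optional, and no sample size or stopping rule rests on it. This stands, and it is why the point is minor.
- The endpoint sentence may concern only whether the substudy is run. This also stands. A reader might infer that the plan states a rule to pick markers after unblinded results; the text permits that but does not say it.
- Some of the plan is already fixed: serum IGF-1, the blood time points, and clinical tumour markers by cohort, the last as measures of non-radiological response. The biological samples manual is not available here, so it cannot be said that no marker list exists anywhere. Protocol 5.6 describes the manual as covering collection, handling and shipment.
- A reader might join the wide laboratory scope to the predictive aim and picture a very large search for predictive markers. The documents do not make that link. The predictive aim belongs to the tissue work, the broad platforms to the blood samples, and the analysis stated for blood is descriptive.
- For objective response in progressive disease, one could argue that background response is rare, so b is small and an association is close to predictive. That needs an assumption from outside the trial about response without the combination at each marker level. It offers nothing for progression-free or overall survival, and the documents do not say which outcome would be used.

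**Conclusion.** The point holds in two limited parts. First, a listed secondary endpoint has no definition beyond a sentence that permits selection on outcome; the sentence is ambiguous, and no error rate for this trial can be attached to it. The 23% to 92% range rests on an assumed number of independent null markers and an assumed 5% level, and it should not be read as the trial's false-positive rate. Second, the protocol's aim of identifying predictive biomarkers cannot be met by one arm; this follows from the design and depends on no assumed number.

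A reader might go further and infer that the trial will report predictive claims. The documents do not support that: the word is an aim in the protocol and synopsis, and the SAP never uses it of its biomarkers. The response-rate analysis and the cohort decisions are unaffected. Severity: minor.

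**What to change.** 1. Synopsis (translational substudy) and protocol 5.6: replace *predictive biomarkers* by *biomarkers associated with response or survival under the combination*.
2. Synopsis, protocol 4.2 and 10.2.2, SAP 1.2.1, 1.2.2 and 2.5.2: move biomarkers from secondary to exploratory. State that the results are hypothesis-generating and will be given as estimates with confidence intervals, without claims of significance.
3. Protocol 10.2.2, SAP 1.2.2 and 2.5.2: remove study results as a ground for choosing markers. Let feasibility decide only whether the substudy is run. If it is run, record and date the list of markers (IGF-1 is already named) and outcomes, with any cut-points, before assay data are linked to response.

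The cost is wording in both documents plus, if the substudy goes ahead, the work of drawing up the list. No patients, visits or samples are added. The downside is a weaker biomarker claim.

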1.3. STUDY METHODS

This is an open labelled, single arm, multicohort phase II multicentre clinical trial of cabozantinib plus atezolizumab in advanced and refractory tumours from endocrine system.

The design includes screening phase, treatment phase (including medical consultation and drug administration Q3w \pm 3 days) unless otherwise specified, disease progression follow up by RECIST 1.1 every 12 weeks, translational research with biopsies and blood samples and long term follow-up.

This is a study with Simon's two-stage design; it requires that an event is observed (confirmed response) in the first nine patients before continuing to the second stage where there is a possible inclusion of 15 additional patients (up to a maximum of 24 patients per cohort).

1.3.1. INCLUSION-EXCLUSION CRITERIA

1.3.1.1 INCLUSION CRITERIA

Patients eligible for inclusion in this study must meet all the following criteria:

1. Male or female subjects \geq 18 years old.
2. Willingness to participate in the study by signing ICF approved by the trial Central Ethic Committee (CEIm).
3. Eastern Cooperative Oncology Group (ECOG) performance status of 0 or 1.
4. Measurable disease per RECIST 1.1 as determined by the investigator.
5. Patients with advanced and progressive neuroendocrine tumors histopathologically confirmed (as per local pathology report), meeting one of the following (according to WHO 2010 classification):
 - a. Cohort 1: Well-differentiated neuroendocrine tumours of the lung and thymus (WHO grade 1 and 2, typical and atypical carcinoids) after progression to somatostatin analogs, targeted agents, PRRT, and/or chemotherapy.
 - b. Cohort 2: Advanced anaplastic thyroid cancer in first-line or after progression to chemotherapy or investigational drugs, that underwent prior primary tumor surgical resection or not. In patients that primary tumor has not been resected, the risk of aerodigestive compression or bleeding should be ruled out to ensure no interference with the administration of the investigational product and undesirable potential side effects related to the route of administration.
 - c. Cohort 3: Adrenocortical carcinoma after progression to chemotherapy and/or mitotane.
 - d. Cohort 4: Pheochromocytoma and paraganglioma after progression to peptide receptor radionuclide therapy (PRRT) if indicated. Prior chemotherapy and biological therapy, such as somatostatin analogs, are allowed.

Sponsor: Grupo Español de Tumores Neuroendocrinos y Endocrinos (GETNE)

- e. Cohort 5: Well-differentiated neuroendocrine tumours of digestive system (WHO grade 1 and 2) after progression to somatostatin analogs, targeted agents, PRRT, and/or chemotherapy.
- f. Cohort 6: Grade 3 neuroendocrine neoplasm (WHO grade 3, including NET and NEC G3) of any origin, excluding small cell lung cancer, after progression to chemotherapy or targeted agents/PRRT.
- 6. Recovery from toxicity related to any prior treatments to \leq Grade 1, unless the AE(s) are clinically non-significant and/or stable on supportive therapy.
- 7. Ability to swallow tablets.
- 8. Adequate normal organ and marrow function as defined below:
 - a. Haemoglobin \geq 9.0 g/dL.
 - b. Absolute neutrophil count (ANC) > 1500 per mm³.
 - c. Platelet count $\geq 100,000$ per mm³.
 - d. Serum bilirubin $\leq 1.5X$ institutional upper limit of normal (ULN) unless liver metastases are present, in which case it must be $\leq 2X$ ULN. This will not apply to patients with confirmed Gilbert's syndrome (persistent or recurrent hyperbilirubinemia that is predominantly unconjugated in the absence of haemolysis or hepatic pathology); however, they will be allowed only in consultation with their physician.
 - e. AST (SGOT)/ALT (SGPT) $\leq 2.5X$ institutional upper limit of normal unless liver metastases are present, in which case it must be $\leq 3X$ ULN.
 - f. Measured creatinine clearance (CL) > 40 mL/min or Calculated creatinine CL > 40 mL/min by the Cockcroft-Gault formula (Cockcroft and Gault 1976) or by 24-hour urine collection for the determination of creatinine clearance:

Males:

$$\text{Creatinine CL (mL/min)} = \frac{\text{Weight (kg)} \times (140 - \text{Age})}{72 \times \text{serum creatinine (mg/dL)}}$$

Females:

$$\text{Creatinine CL (mL/min)} = \frac{\text{Weight (kg)} \times (140 - \text{Age}) \times 0.85}{72 \times \text{serum creatinine (mg/dL)}}$$

1.3.1.2 EXCLUSION CRITERIA

Patients that meet any of the following criteria will be excluded from the study:

1. Prior treatment with cabozantinib or any immune checkpoint inhibitor therapy (e.g, CTLA4, PD-1, or PD-L1 targeting agent).
2. Receipt of any type of small molecule kinase inhibitor (including investigational kinase inhibitor) within 2 weeks or 5 half-lives of the agent, whichever is longer. Patients should have been out of mitotane for at least 4 weeks.

Sponsor: Grupo Español de Tumores Neuroendocrinos y Endocrinos (GETNE)

3. Receipt of any type of anticancer antibody (including investigational antibody) or systemic chemotherapy within 2 weeks before starting treatment.
4. Current or prior use of immunosuppressive medication within 2 weeks before the first dose of cabozantinib and atezolizumab, with the exceptions of intranasal and inhaled corticosteroids or systemic corticosteroids at physiological doses, which are not to exceed 10 mg/day of prednisone, or an equivalent corticosteroid.
5. Active or prior documented autoimmune disease within the past 2 years NOTE: Subjects with vitiligo, Grave's disease, or psoriasis not requiring systemic treatment (within the past 2 years) are not excluded.
6. Active or prior documented inflammatory bowel disease (e.g., Crohn's disease and ulcerative colitis).
7. History of allogeneic organ transplant.
8. Subjects having a diagnosis of immunodeficiency or are receiving systemic steroid therapy or any other form of immunosuppressive therapy within 28 days prior to the first dose of trial treatment.
9. Receipt of radiation therapy for bone metastasis within 2 weeks or any other radiation therapy within 4 weeks before inclusion. Subjects with clinically relevant ongoing complications from prior radiation therapy that have not completely resolved are not eligible (e.g, radiation esophagitis or other inflammation of the viscera).
10. Known brain metastases or cranial epidural disease unless adequately treated with radiotherapy and/or surgery (including radiosurgery) and stable for at least 4 weeks before inclusion. Eligible subjects must be neurologically asymptomatic and without corticosteroid treatment at the time of study treatment.
11. Concomitant anticoagulation with oral anticoagulants (e.g, warfarin, direct thrombin and factor Xa inhibitors) or platelet inhibitors (e.g, clopidogrel), except for the following allowed anticoagulants:
 - Low-dose aspirin for cardioprotection (per local applicable guidelines) and low-dose low molecular weight heparins (LMWH).
 - Anticoagulation with therapeutic doses of LMWH in subjects without known brain metastases and who are on a stable dose of LMWH for at least 6 weeks before inclusion and who have had no clinically significant hemorrhagic complications from the anticoagulation regimen or the tumour.
12. The subject has uncontrolled, significant intercurrent or recent illness including, but not limited to, the following conditions:
 - a. Cardiovascular disorders:
 - i. Class 3 or 4 congestive heart failure as defined by the New York Heart Association, unstable angina pectoris, and serious cardiac arrhythmias.
 - ii. Uncontrolled hypertension defined as sustained blood press > 150 mm hg systolic or > 100 mm hg diastolic despite optimal antihypertensive treatment.

Sponsor: Grupo Español de Tumores Neuroendocrinos y Endocrinos (GETNE)

- iii. Stroke (including transient ischemic attack [TIA]), myocardial infarction, other ischemic event, or thromboembolic event (e.g. deep venous thrombosis [DVT] and pulmonary embolism) within 6 months before inclusion. Subjects with a more recent diagnosis of DVT are allowed if stable, asymptomatic, and treated with LMWH for at least 6 weeks before study treatment.
- b. Gastrointestinal disorders (e.g. malabsorption syndrome or gastric outlet obstruction) including those associated with a high risk of perforation or fistula formulation:
 - i. Tumours invading the GI tract, active peptic ulcer disease, inflammatory bowel disease, ulcerative colitis, diverticulitis, cholecystitis, symptomatic cholangitis or appendicitis, acute pancreatitis or acute obstruction of the pancreatic or biliary duct, or gastric outlet obstruction.
 - ii. Abdominal fistula, GI perforation, bowel obstruction, or intra-abdominal abscess within 6 months before inclusion. Note: complete healing of an intra-abdominal abscess must be confirmed prior to start of the treatment.
- c. Clinically significant hematemesis or hemoptysis of > 0.5 teaspoon (> 2.5 ml) of red blood or history of other significant bleeding within 3 months before treatment.
- d. Cavitating pulmonary lesion(s) or known endobronchial disease manifestation.
- e. Lesions invading major pulmonary blood vessels.
- f. Other clinically significant disorders such as:
 - i. Active infection requiring systemic treatment, infection with human immunodeficiency virus or acquired immunodeficiency syndrome-related illness, or chronic hepatitis B or C infection.
 - ii. Serious non-healing wound/ulcer/bone fracture.
 - iii. Moderate to severe hepatic impairment (child-pugh B or C).
 - iv. Requirement for hemodialysis or peritoneal dialysis.
 - v. Uncontrolled diabetes mellitus.
 - vi. History of solid organ transplantation.
- 13. Major surgery (e.g. GI surgery and removal or biopsy of brain metastasis) within 8 weeks before inclusion. Complete wound healing from major surgery must have occurred 4 weeks before study treatment and from minor surgery (e.g. simple excision, tooth extraction) at least 10 days before study treatment. Subjects with clinically relevant ongoing complications from prior surgery are not eligible.
- 14. Corrected QT interval calculated by the Fridericia formula (QTcf) > 500 ms within 28 days before study treatment.

Note: if a single ECG shows a QTcf with an absolute value > 500 ms, two additional ECGs at intervals of approximately 3 min must be performed within 30 min after the initial ECG, and the average of these 3 consecutive results for qtcf will be used to determine eligibility.

- 15. Pregnant or lactating females.

Sponsor: Grupo Español de Tumores Neuroendocrinos y Endocrinos (GETNE)

16. Inability to swallow tablets.
17. Previously identified allergy or hypersensitivity to components of the study treatment formulations.
18. Diagnosis of another malignancy within 3 years before study treatment, except for superficial skin cancers, or localised, low grade tumours deemed cured and not treated with systemic therapy.

